## 2. Study Objectives

The aim of our study is to determine the safety and efficacy of an early goal-directed preload and afterload decrement with a target systolic blood pressure of 90 mm Hg to 110 mm Hg by aggressive vasodilatation versus standard medical care in a non-ICU setting in patients with acute HF.

### 2.1 Primary Endpoints

- Death or HF re-hospitalization at 180 days.

### 2.2 Secondary Endpoints

- All-cause mortality at 180 days.
- HF re-hospitalization at 180 days.
- Death or re-hospitalization from all causes at 180 days.
- Need for ICU admission during initial hospitalization.
- Acute coronary syndrome during initial hospitalization.
- Symptomatic hypotension during initial hospitalization.
- B-type natriuretic peptide (BNP) and creatinine level at 48 h and at discharge.
- Changes in circumferences of both legs and central venous pressure during hospitalization.
- Change in patient-assessed dyspnea at 48 h and prior to discharge.
- Blood pressure course over the first 6 days.
- Time to disappearance of a third heart sound (if present initially).
- Time to discharge.
- In-hospital days for HF at 180 days and 360 days.
- Total treatment cost at 180 days and 360 days.
- Functional status at 180 days and 360 days.
- Quality of life at 180 days and 360 days.
- Fractures due to falls within 180 days and 360 days.
- Death or HF re-hospitalization at 360 days.

Predefined subgroup analyses will be performed in patients younger or older than 75 years of age, men and women, systolic (LVEF < 45%) HF and HF with preserved LVEF, systolic blood pressure at presentation lower or higher than 140 mm Hg, coronary artery disease present or not, BNP levels lower or higher than 1000 pg/ml and isolated or concurrent right HF.

### 3. Study Design

This trial is designed as a prospective, randomized, controlled multicenter study coordinated by the University Hospital Basel. Patients will be enrolled in the emergency departments of participating sites:

- University Hospital Basel, Switzerland  
([name], FESC, Professor of Medicine)
- Lucerne Cantonal Hospital, Switzerland  
([name], FESC, Professor of Medicine)
- Cantonal Hospital Aarau, Switzerland  
([name], Professor of Medicine)
- Cantonal Hospital St. Gallen, Switzerland  
([name], Professor of Medicine; [name])
- Hospital Clinic of the Faculty of Medicine University of São Paulo, Brazil  
([name], MD)
- University Medicine Mainz, Federal Republic of Germany  
([name], Professor of Medicine)
- Faculty of Medicine University of Latvia, Riga, Latvia  
([name], MD, Professor of Medicine)
- Hull and East Yorkshire Hospitals, United Kingdom  
([name], Professor of Medicine)
- University Medicine Nürnberg, Federal Republic of Germany  
([name], Professor of Medicine)
- Mafraq Hospital Abu Dhabi, United Arab Emirates  
([name] [name])
- Hospital Universitari Germans Trias i Pujol Barcelona, Spain  
([name], Professor of Medicine)
- Hospital de la Santa Creu i Sant Pau Barcelona, Spain  
([name], Professor of Medicine)
- University Hospital Belgrade, Republic of Serbia  
([name], Professor of Medicine)
- University Hospital “Tsaritsa Joanna-ISUL” Sofia, Bulgaria  
([name] PhD, Professor and Chief of Cardiology)
- National Transport Hospital “Tsar Boris III” Sofia, Bulgaria  
([name] PhD, Professor of Medicine)
- 5-th Multifunctional Hospital for Active Treatment Sofia, Bulgaria  
([name])
- University Hospital “Alexandrovska” Sofia, Bulgaria  
([name] PhD, Professor of Medicine)

If necessary, further study sites can be enrolled.

Consulting experts (in alphabetical order):

- [name] (MD, Professor of Medicine),  
Basel, Switzerland
- [name] (MD, FESC, FACC, Professor of Cardiology),  
Basel, Switzerland
- [name] (MD, Extraordinary Professor of Cardiology),  
Maastricht, Netherlands
- [name] (MD, Professor of Anesthesiology and Critical Care  
Medicine), Paris, France
- [name] (MD, FESC, FACC, FAHA, Professor of Cardiology),  
Basel, Switzerland
- [name] (MD, PhD, Professor of Medicine),  
Basel, Switzerland
- [name] (PhD in Mathematics),  
Basel, Switzerland

## 4. Study Subjects

To be enrolled in the study, each patient must meet all of the following inclusion criteria and none of the following exclusion criteria.

### 4.1 Patients Selection and Inclusion Criteria

Acute HF expressed by acute Dyspnea New York Heart Association (NYHA) class III or IV and a BNP level  $\geq 500$  ng/l (or NTpro-BNP level  $\geq 2000$  ng/l). Due to inverse association of BNP levels and BMI, for Patients presenting with BMI of  $\geq 35$  kg/m^2, the BNP cut point is  $\geq 350$  ng/l (or NTpro-BNP level  $\geq 1400$  ng/l) (32–34). Only NTpro-BNP, but not BNP, can be used for the inclusion of patients treated with LCZ696 (“Entresto”) (35,36). The diagnosis of acute HF is additionally based on typical symptoms and clinical findings, supported by appropriate investigations such as ECG, chest X-ray, and Doppler-echocardiography as recommended by current ESC guidelines on the diagnosis and treatment of acute HF(1,2). For inclusion in this study, all of the following criteria must apply:

- Acute HF.
- Age at least 18 years.
- Informed consent.
- Negative pregnancy test (only in female patients younger than 60 years).

### 4.2 Exclusion Criteria

- Cardiopulmonary resuscitation less than 7 days ago.
- Cardiogenic shock, ST-elevation myocardial infarction, or other clinical conditions that require immediate ICU admission or urgent PTCA.
- Systolic blood pressure lower than 100 mm Hg at presentation.
- Primary rhythmogenic cause of acute decompensation (ventricular tachycardia, reentry tachycardia, atrial fibrillation or atrial flutter with a ventricular rate exceeding 140 beats per minute).
- Non-ST-elevation myocardial infarction as primary diagnosis.
- Severe aortic or mitral stenosis.
- Adult congenital heart disease as primary cause of acute HF.
- Hypertrophic obstructive cardiomyopathy.
- Isolated right ventricular failure due to pulmonary hypertension.
- Chronic kidney disease with creatinine levels  $> 250$   $\mu$ mol/l.
- Bilateral renal artery stenosis.
- Severe sepsis or other causes of high output failure.
- Liver Cirrhosis Child-Pugh class C.
- Systemic Lupus erythematosus and related diseases.
- Acute aortic dissection.

- Porphyria.
- Previous adverse reactions to nitrates.
- Known hypersensitivity to hydralazine or dihydralazine.
- Patient in an emergency situation resulting in an inability to give informed consent.

## 5. Procedures

Figure 4: Study procedures.

## Diagnosis

To ensure maximal diagnostic accuracy at the time of inclusion in this study, the diagnosis of acute HF will be established as recommended by the current guidelines of the European Society of Cardiology for acute HF(1,2,37). The diagnosis of HF is based on patient history, physical examination, chest X-ray, ECG and BNP testing. Some patients will also have echocardiography performed in the acute setting. The diagnosis of HF results from a careful integration of the results of all of these investigations (Figure 4). The following findings suggest the presence of HF: history of HF, orthopnea, paroxysmal nocturnal dyspnea, dyspnea on exertion, distended neck veins, pulmonary rales, edema, laterally displaced and increased apical impulse, third heart sound, pathological ECG, radiologic signs of congestion or cardiomegaly in chest X-ray, BNP levels above 500 ng/l (respectively NT-proBNP levels above 2000 ng/l) and 350 ng/l if BMI  $\geq$  35 kg/m^2 (respectively NT-proBNP levels above 1400 ng/l), as well as severely impaired systolic or diastolic left ventricular function. If there are no clear clinical signs or symptoms (e. g. rales) or radiological findings (e. g. signs of congestion or cardiomegaly) ruling out an isolated right heart failure, echocardiography should be performed to confirm that there is no isolated right heart failure due to pulmonary hypertension.

When after integration of these findings the ED physicians quantifies the likelihood for the presence of HF using a visual analogue scale (38,39) as 80% or higher, a senior ED physician or a board certified cardiologist will examine the patient. When this one agrees with the proposed diagnosis and also judges the diagnosis of acute HF to be 80% or higher, the patient will be considered for inclusion in the study.

## Study inclusion and Randomization

Patients who fulfil all of the inclusion criteria and none of exclusion criteria will thoroughly be informed about study protocol and informed consent will be obtained.

Group assignment will be accomplished with the use of a computer-generated randomization scheme in a 1:1 ratio. Randomization will be stratified for enrolling site and the severity of HF as quantified by the BNP level (below or above 1000 ng/l/1000 ng/l) or NTpro-BNP level (below or above 4000 ng/l). Patients will be randomized to either the early goal directed group or the control group. The initial therapeutic goal is identical in both groups: the rapid resolution of dyspnea at rest.

## Study Therapy Early Goal-Directed Group

Early goal-directed preload and afterload decrement with a target systolic blood pressure of 90 mm Hg to 110 mm Hg for the entire hospitalization. This blood pressure target is considered to represent the maximal feasible afterload decrement without impairment of critical organ perfusion (40). This pathophysiologic goal is pursued by predominately applying nitrates, ACE-inhibitors and ARBs at maximal tolerable (avoiding arterial hypovolemia and inadequate arterial perfusion pressure) doses.

The treatment schedule is displayed in Figure 5a. Accordingly, on day 1 (0 h till 24 h) treatment will be started with one capsule of sublingual nitrates (containing usually 0.8 mg glyceryl trinitrate) or two applications of nitrospray (containing usually 0.4 mg

glyceryl trinitrate per application) in combination with transdermal nitrates (for example Nitroderm TTS® 10 mg / 24h) in a dosage between 40 to 80 mg / 24 h depending on admission systolic blood pressure. 10 and 20 minutes after the initial sublingual nitrates capsule or nitrospray application, one additional capsule of sublingual nitrates (containing usually 0.8 mg glyceryl trinitrate) or two applications of nitrospray (containing usually 0.4 mg glyceryl trinitrate per application) will be administered (in total three capsules sublingual nitrates or six applications of nitrospray). After 6 hours a dose adjustment of the transdermal nitrates dependent on systolic blood pressure will be performed (Figure 5a). On day 1 and 2, transdermal nitrates will be applied as continuous therapy for 24 hours each patch. In patients without severe renal dysfunction (defined as calculated glomerular filtration rate below 30 ml/min) and without evidence of an acute coronary syndrome (accompanying chest pain, new ECG changes, elevated cardiac Troponin T), hydralazine will be added orally to achieve an early maximal vasodilative effect and to avoid tolerance to nitrates. Hydralazine will be administered in a fix dosage of 25 mg every 6 hours (1 - 1 - 1 - 1) for the first 48 hours after study inclusion. Patients with evidence for an acute coronary syndrome (Cave: “coronary steal”) or with severe renal dysfunction (Cave: accumulation) will not receive hydralazine, but nitrates only.

On day 2 (24 h till 48h) the dosage of transdermal nitrates will be adjusted according to systolic blood pressure. In addition, at 24 hours after study inclusion, therapy with a peroral ACE-inhibitor or in case of ACE-inhibitor intolerance an ARB will be initiated. Should the patient be already on an ACE-inhibitor, the dosage remains unchanged for the first 24 hours. On day 2 (after 24 hours) the ACE-inhibitor will be up-titrated according to therapy schedule (Figure 5a) starting from day 2. Thereby, the up-titration will be performed on the top of the precedent ACE-inhibitor / ARB dosage. Should the patient be already on a maximal dosage of an ACE-inhibitor, an ARB will be added at low dose once daily and up-titrated according to the therapy schedule. In patients with chronic HF and a LVEF below 35%, the treating physician may at any time (both in-hospital and after hospitalization) consider to replace a preexisting therapy with an ACE-inhibitor or ARB with LCZ696 as recommended in the 2016 ESC guidelines (37). Should the patient already be on LCZ696 (“Entresto”), the dosage remains unchanged for the first 24 hours. On day 2 (after 24 h) the dose of LCZ696 will be up-titrated by 25% if not already on target dose (200 mg b.i.d.). Again, the dose should be increased by 25% at the end of hospitalization (if not already at 200 mg b.i.d.).

Intervention group	day 1 at hospital admission		day 1 6 h after admission		
	< 130 	> 130 	90 - 110	111 - 130	> 130
systolic blood pressure [mm Hg]	< 130 	> 130 	90 - 110	111 - 130	> 130
per oral Glyceryl trinitrate capsule (i.e. Nitroglycerin Streuli ® ) 0.8 mg  or Spray (i.e. Corangin Nitrospray ® ) 0.4mg	3 or 6 applic.	3 or 6 applic.			
transdermal Glyceryl trinitrate (i.e. Nitroderm ® TTS) [mg / 24 h]	40 - 60	60 - 80	+ 0	+ 20 - 40	+ 20 - 60
Hydralazine (i. e. Hydrapres ® ) 25 mg	1 - 1 - 1 - 1	1 - 1 - 1 - 1	1 - 1 - 1 - 1	1 - 1 - 1 - 1	1 - 1 - 1 - 1
Ramipril (i. e. Triatec ® ) [mg/d] 					
Lisinopril (i. e. Zestril ® ) [mg/d] 					
Enalapril (i. e. Reniten ® ) [mg/d] 					

-  The lowest blood pressure value measured at the emergency department before study inclusion will be considered.
-  The first capsule should be administered at study inclusion, 10 and 20 minutes after the first capsule one more capsule should be administered (total three capsules).
-  Only one ACE-inhibitor should be started.
-  ARB will only be administered initially if patients already receive the maximal dosage of an ACE-inhibitor or if ACE-inhibitor intolerance is known.
-  An additional treatment with ARB should be considered (according to the ARB up-titration days 2 to 7).

Captopril (i. e. Capoten®) [mg/d] 					
Candesartan (i. e. Atacand®) [mg/d] 					
Losartan (i. e. Cozaar®) [mg/d] 					

**Figure 5a:** Treatment algorithm for the early goal-directed therapy group.

Intervention group continuation	day 2 24 h till 48 h after admission				day 3 48 h till 72 h after admission			
	90 - 110	111 - 130	131 - 150	> 150	90 - 110	111 - 130	131 - 150	> 150
systolic blood pressure [mm Hg]	90 - 110	111 - 130	131 - 150	> 150	90 - 110	111 - 130	131 - 150	> 150
transdermal Glyceryl trinitrate (i.e. Nitroderm® TTS) [mg / 12 h]	+ 20 - 40	+ 20 - 60	+ 40 - 80	+ 40 - 80	50% of day 2	50% of day 2	75% of day 2	100% of day 2
Hydralazine (i. e. Hydrapres®) 25 mg	1 - 1 - 1 - 1	1 - 1 - 1 - 1	1 - 1 - 1 - 1	1 - 1 - 1 - 1				
Ramipril (i. e. Triatec®) [mg/d] 	1.25	1.25	2.5	2.5	2.5 - 3.75	2.5 - 3.75	2.5 - 5	2.5 - 5
Lisinopril (i. e. Zestril®) [mg/d] 	2.5	2.5	5	5	2.5 - 5	5 - 7.5	10 - 15	10 - 20
Enalapril (i. e. Reniten®) [mg/d] 	5	5	10	10	5 - 10	5 - 10	10 - 15	10 - 20
Captopril (i. e. Capoten®) [mg/d] 	37.5	37.5	50	50	37.5 - 50	37.5 - 50	50 - 75	50 - 75
Candesartan (i. e. Atacand®) [mg/d] 	4	4	8	8	8 - 16	8 - 16	16 - 24	16 - 24
Losartan (i. e. Cozaar®) [mg/d] 	25	25	50	50	25 - 50	25 - 50	50 - 75	50 - 75

Intervention group continuation	day 4 72 h till 96 h after admission				day 5 96 h till 120 h after admission			
	90 - 110	111 - 130	131 - 150	> 150	90 - 110	111 - 130	131 - 150	> 150
systolic blood pressure [mm Hg]	90 - 110	111 - 130	131 - 150	> 150	90 - 110	111 - 130	131 - 150	> 150
transdermal Glyceryl trinitrate (i.e. Nitroderm® TTS) [mg / 12 h]	25% of day 2	25% of day 2	50% of day 2	75% of day 2			25% of day 2	50% of day 2
Ramipril (i. e. Triatec®) [mg/d] 	3.75 - 5	3.75 - 5	5 - 7.5	5 - 7.5	5 - 7.5	5 - 7.5	7.5 - 10	7.5 - 10
Lisinopril (i. e. Zestril®) [mg/d] 	5 - 10	10 - 15	15 - 20	15 - 25	10 - 15	15 - 20	20 - 30	20 - 30
Enalapril (i. e. Reniten®) [mg/d] 	10 - 15	10 - 15	15 - 20	20 - 30	15 - 20	15 - 20	20 - 30	30 - 40
Captopril (i. e. Capoten®) [mg/d] 	50 - 75	50 - 75	75 - 100	75 - 100	75 - 100	75 - 100	100 - 150	100 - 150
Candesartan (i. e. Atacand®) [mg/d] 	12 - 24	12 - 24	16 - 24	16 - 24	16 - 24	24 - 32	24 - 32	24 - 32
Losartan (i. e. Cozaar®) [mg/d] 	50 - 75	50 - 75	75 - 100	75 - 100	75 - 100	75 - 100	75 - 100	75 - 100

Intervention group continuation	day 6 120 h till 144 h after admission				day 7 144 h till 168 h after admission			
	90 - 110	111 - 130	131 - 150	> 150	90 - 110	111 - 130	131 - 150	> 150
systolic blood pressure [mm Hg]	90 - 110	111 - 130	131 - 150	> 150	90 - 110	111 - 130	131 - 150	> 150
transdermal Glyceryl trinitrate (i.e. Nitroderm® TTS) [mg / 12 h]								
Ramipril (i. e. Triatec®) [mg/d] 	7.5 - 10	7.5 - 10	10	10 	10	10	10 	10 
Lisinopril (i. e. Zestril®) [mg/d] 	15 - 20	20 - 30	20 - 30	30 	20 - 30	20 - 30	30 	30 
Enalapril (i. e. Reniten®) [mg/d] 	20 - 30	20 - 30	30 - 40	40 	30 - 40	30 - 40	40 	40 
Captopril (i. e. Capoten®) [mg/d] 	100 - 150	100 - 150	150	150 	150	150	150 	150 
Candesartan (i. e. Atacand®) [mg/d] 	24 - 32	24 - 32	32	32	24 - 32	24 - 32	32	32
Losartan (i. e. Cozaar®) [mg/d] 	75 - 100	75 - 100	100	100	75 - 100	100	100	100

### Important Treatment Rules

- ACE-inhibitor can be administered once or twice per day. ARB should be administered only once a day.
- If Patient is already on ACE-inhibitor or ARB continue dosage unchanged during day 1 and perform up-titration following day 2 till 7 schedule.
- If the patient is already treated with another ACE-inhibitor / ARB than listed in the schedule, previously prescribed ACE-inhibitor / ARB should be continued unchanged during day 1. A daily up-titration of approximate 50% (25% to 75% depending on blood pressure response) starting from day 2 is recommended. The maximal dosage should be achieved at day 5 to 7 of treatment if well tolerated.
- If creatinine levels rise more than 50% from baseline continue ACE-inhibitor / ARB in unchanged dosage to creatinine levels begin to decline. Then continue up-titration according to the treatment schedule.
- If creatinine levels rise more than 100% from baseline reduce ACE-inhibitor / ARB treatment by 50% and continue therapy with unchanged dosage until creatinine levels decline more than 30%.
- Treatment with any diuretics or aldosterone-antagonists at any time is at discretion of treating physician and not determined by the study protocol.

**Figure 5a:** Treatment algorithm for the early goal-directed therapy group (continuation).

On day 3 a further up-titration of the ACE-inhibitor / ARB depends on systolic blood pressure according to Figure 5a will be performed. In patients on LCZ696, the dose of LCZ696 remains unchanged. The dosage of transdermal nitrates will be gradually decreased from day 3 till hospital discharge (Figure 5a). Also, intermittent dosing (12 hours nitrates, 12 hours nitrate-free period) will be used from day 3 on. Typically, we would use in half the dose applied at day 2 and apply the patches from 8:00 h am till 8:00 h pm.

On day 4 till day 7 a further up-titration of the ACE-inhibitor / ARB dependent on systolic blood pressure according to Figure 5a will be performed. In patients on LCZ696 the dose of LCZ696 will be up-titrated by again 25% if not already on target dose (200 mg twice daily).

If patients are pre-treated with either ACE-inhibitor or ARB, therapy with these agents will be continued during the first 24 hours at the pre-existing dosage and afterwards up-titrated following the therapy schedule starting with day 2. Should the patient be already treated with another ACE-inhibitor / ARB than listed in the therapy schedule (Figure 4), the previously prescribed ACE-inhibitor / ARB will be continued in an unchanged dosage. The up-titration will then be performed in a comparable way like demonstrate in the schedule (Figure 5a). A daily up-titration of approximate 50% (25% to 75% depending on blood pressure response) starting from day 2 is recommended. The maximal dosage should be achieved after 5 to 7 days of treatment if well tolerated.

Hydralazine Hydrochlorid:

Until December 2012 Hydralazine Hydrochlorid was administered using Apresoline® 25mg (Hydralazine Hydrochlorid). From January 2013 Hydralazine Hydrochlorid will be administered using Hydrapres® 25mg (Hydralazine Hydrochlorid) as the former no longer was commercially available.

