### **Study Therapy Control Group**

The current guidelines of the European Society of Cardiology do not recommend the use of ACE-inhibitors or ARB in the early stabilization of patients with acute HF (41). (37). The administration of previously prescribed ACE-inhibitors or ARB should be continued on admission with AHF, except in the presence of hemodynamic instability, hyperkalemia or severely impaired renal function. In these cases, the daily dosage of oral therapy may be reduced or stopped temporarily until the patient is stabilized. In the absence of a prescription, an initiation of the medication before discharge from hospital and up-titration every two to four weeks is recommended (37). Accordingly, patients in the control group will receive (1,2) oxygen application, treatment with diuretics based on extent of fluid overload and recent weight gain. The dosage thereby will be adjusted to renal function. Further on, after 24 to 48 hours, treatment with an ACE-inhibitor (or ARB) will be started in low dosages displayed in Figure 5b. After six to eight days of treatment, dosage of the ACE-inhibitor / ARB will be up-

titrated following the schedule displayed in Figure 5b dependent on hemodynamic and renal tolerance. As in the Intervention group, in patients with chronic HF and a LVEF below 35%, the treating physician may at any time (both in-hospital and after hospitalization) consider to replace a preexisting therapy with an ACE-inhibitor or ARB with LCZ696 as recommended in the 2016 ESC guidelines (36). Should the patient already be on LCZ696 (“Entresto”), the dosage will remain unchanged for the first 4 to 5 days with the option of increasing the dose by 25% at the end of hospitalization (if not already at 200 mg b.i.d).

Transdermal nitrates can be used, but only in the doses currently approved in Switzerland (e. g. Nitroderm TTS 5 mg / 12 h or 10 mg / 12h). The use of nitrates or hydralazine in higher doses is strongly discouraged. The use of a specific blood pressure target is up to the discretion of the treating physician.

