### **Patient Safety: Worsening Renal Function**

Some rise in creatinine and blood urea nitrogen levels is commonly seen in patients with acute HF. Often it is not possible to identify a single cause, but hypovolemia induced by diuretic treatment, low output as part of acute HF, renal venous congestion or initiation of ACE-inhibitors / ARB may play a role. Regarding the up-titration of ACE-inhibitors / ARB current guidelines suggest that changes in creatinine or blood urea nitrogen levels should not be considered clinically important unless they are rapid and substantial (41). Accordingly, a creatinine rise less than 50% from baseline values will be carefully monitored without adjustment of treatment schedule. In case of a rise of more than 50% of the baseline value, the treatment with ACE-inhibitors / ARB will be continued without augmentation and creatinine levels will be monitored every 24 hours to 48 hours. As soon as creatinine levels begin to decline, dosage of ACE-inhibitor / ARB will be up-titrated according to the treatment schedule (Figures 4a / 4b). In case of acute renal injury, defined as a doubling in serum creatinine levels compared to baseline levels (42), the following procedural schedule will be applied: A 50% reduction of the last ACE-inhibitor / ARB dosage will be performed and creatinine levels will be measured 24 hours to 48 hours later. When creatinine levels continue to rise despite this measure, a further stepwise decrease of 50% of the ACE-inhibitor / ARB is scheduled and will be repeated every 48 hours until creatinine levels begin to decline. When creatinine levels remain unchanged or decrease less than 30% of peak level, the current dosage of ACE-inhibitor / ARB will remain unchanged. As soon as creatinine levels decrease at least 30% to peak value, the initial study therapy schedule will be continued (Figures 4a / 4b). As the

dose of diuretics is an important contributor to renal injury, diuretic dose will also be reduced by at least 50% in patients with renal injury.

If systolic blood pressure still persists over 140 mm Hg despite the treatment schedule described above during day 3 to 6, higher doses of ACE-inhibitors or ARBs are recommended. The addition of a calcium-channel blocker (preferably amlodipine, Norvasc®(43) can be considered alternatively. The use of beta-blockers and spironolactone will be identical to that described in the control group.

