### **General Procedure for Both Groups**

At any time in the study the use of further treatment including loop diuretics, aldosterone antagonists, morphine or other drugs or non-pharmacological therapies (including non-invasive ventilation) will always be dependent on the clinical conditions and will be at the discretion of the treating physician.

Non-invasive hemodynamic monitoring will be performed every 10 to 30 minutes during the first hour, every 30 to 90 minutes in the second to the fourth hour, and every 6 to 8 hours for the rest of the hospitalization as currently in practice at the enrolling institutions. Continuous recording of a three-channel ECG and transdermal oxygen saturation provided by automated monitoring systems will be applied as clinically indicated.

At the time of initial presentation and before discharge the patient leg circumference will be measured at three distinct points on either side: 10 cm distal from the caput fibulae, 5 cm above the ankles and at the middle of the metatarsi. The points of measurement will be marked. A special tape measure incorporating a spring exercising constant tension will be used ensuring a measurement independent of the strain applied by the investigator. Simultaneously and when possible, the central venous pressure will be obtained with a high resolution ultrasound imaging device combined with a translucent pressure manometer.

In addition, 15 ml of serum, EDTA plasma and urine will be collected at five time points (at baseline, at day 1, day 2, day 6 and discharge) for the measurement of biomarkers such as BNP, NT-proBNP, mid-regional pro-atrial natriuretic peptide, pro-adrenomedullin, copeptin, N-GAL, Cystatin C, Troponin T, and pro-endothelin that also reflect the response to treatment. The determination of NT-proBNP, mid-regional pro-atrial natriuretic peptide, pro-adrenomedullin, copeptin, N-GAL, Cystatin C, Troponin T, and pro-endothelin and pro-endothelin will be performed collectively after hospital discharge of patients and has no effect on patient treatment.

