Transthoracic echocardiography (TTE) for the detailed assessment of systolic, diastolic, and valvular function will be performed as clinically indicated in the majority of patients. Response to therapy will be documented by daily clinical patient assessment using a predefined questionnaire as well as a visual analogue scale to record subjective course of dyspnea. Periodical measurements of electrolytes (sodium, potassium) and creatinine at study inclusion, every 24 to 72 hours during the first week and at discharge will be accomplished.

In the further course of treatment (usually one or two days before discharge), a beta-blocker will be added to this therapy at very low dose. Augmentation of the beta-blocker dosage will only be performed after discharge during the outpatient phase. Spironolactone (an aldosteron-receptor-antagonist) may be added in patients who remain in NYHA classes III and IV and in patients with low potassium concentration at presentation, as long as they have a serum creatinine below 150 µmol/l.

Despite early blood pressure intervention in the study group, special attention will be given to the final drug-treatment in both study groups. As ACE-inhibitors / ARB and beta-blockers provide the best documented survival benefit in patients with HF (3,7), initiation of a beta-blocker before hospital discharge will be strongly endorsed, and treatment of an equal percentage of patients in both arms with these two agents remains crucial.

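### When creatinine has doubled and keeps rising, the rules printed with Figure 5a hold the ACE-inhibitor/ARB dose, while the protocol's renal-safety section cuts it again

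*Combined protocol and SAP*

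**What the plan says.** All of the dosing text is in Protocol section 5.

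**ACE-inhibitor/ARB dose.** The Important Treatment Rules, printed with the intervention-arm algorithm in Figure 5a, cover a creatinine rise above 100% of baseline. The instruction is to "reduce ACE-inhibitor / ARB treatment by 50% and continue therapy with unchanged dosage until creatinine levels decline more than 30" per cent. Patient Safety: Worsening Renal Function covers the same event, which it defines as a doubling of creatinine. It also halves the dose and then adds that "creatinine levels will be measured 24 hours to 48 hours later". It continues: "When creatinine levels continue to rise despite this measure, a further stepwise decrease of 50% of the ACE-inhibitor / ARB is scheduled". That step repeats every 48 hours until creatinine begins to decline. The dose is held if creatinine is unchanged or has fallen by less than 30% of its peak. The schedule resumes once it has fallen by at least 30% from peak.

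**Diuretics.** The Important Treatment Rules state: "Treatment with any diuretics or aldosterone-antagonists at any time is at discretion of treating physician and not determined by the study protocol". General Procedure for Both Groups says that further treatment, loop diuretics included, "will always be dependent on the clinical conditions and will be at the discretion of the treating physician", at any time in the study. The Protocol Summary (Methodology) and SAP section 1 (Study synopsis) also leave the timing and dose of diuretics to the physician in both groups. Against these, the renal section states that "diuretic dose will also be reduced by at least 50% in patients with renal injury".

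**The concern.** The rules printed with the dosing table are the ones a ward clinician is most likely to have to hand. For a patient whose renal function keeps worsening, they give the less protective instruction. They do more than shorten the renal section: telling the clinician to keep the dose unchanged until creatinine falls is a positive instruction, and it excludes a second cut.

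The patients concerned are in the arm with daily up-titration and a systolic target of 90 to 110 mm Hg. Protocol section 6 names hypotension with reduced blood flow to the kidneys and other major organs as the main potential adverse event. The sponsor wrote an escalating dose reduction for this situation, and the bullet beside the table contradicts it. No text says which of the two prevails.

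**Working it through.** No statistical figure is involved. The check sets the two rules side by side, state by state, and then works out the dose fractions.

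**ACE-inhibitor/ARB after creatinine doubles**

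| State | Important Treatment Rules (Figure 5a) | Worsening Renal Function | Agreement |
|---|---|---|---|
| Creatinine doubles | Cut 50% | Cut 50% | Yes |
| Recheck | No time given | 24 to 48 h | Omission only |
| Still rising after the first cut | Hold | Cut a further 50%, repeated every 48 h until decline begins | **No** |
| Unchanged, or down less than 30% | Hold | Hold (30% measured from peak) | Yes |
| Down 30% | Hold ends after a fall of more than 30% | Schedule resumes after a fall of at least 30% from peak | Trivial wording difference |

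Only the third row is a contradiction.

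**Size in that row.** The fraction of the pre-injury dose left after k halvings is 0.5^k.
- Figure 5a rule: one halving, then hold. 0.5^1 = 50%, however long creatinine rises.
- Renal section after one further step: 0.5^2 = 25%. The ratio is 50/25 = 2.
- Renal section after two further steps: 0.5^3 = 12.5%. The ratio is 50/12.5 = 4.

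With top doses from Figure 5a:
- Ramipril 10 mg/d: held at 5 mg under the Figure 5a rule; 2.5 mg after one further step under the renal section.
- Enalapril 40 mg/d: held at 20 mg under the Figure 5a rule; 20, then 10, then 5 mg under the renal section.

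**Diuretics in renal injury.** The required cut is at least 50% in the renal section. None is required in the Protocol Summary, the Important Treatment Rules, General Procedure for Both Groups or SAP section 1. The General Procedure wording mentions clinical conditions, but it still gives the decision to the physician at any time, so it conflicts in the same way as the bullet. The count is four statements against one, with no order of precedence.

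**Clerical items**
- The renal section refers to Figures 4a and 4b, which do not exist. Figure 4 shows study procedures; the schedules are Figures 5a and 5b.
- The text after Figure 5a cites Figure 4 for the therapy schedule, but the next sentence cites Figure 5a correctly.
- The patch row shared by days 2 and 3 is labelled in mg per 12 h. The early goal-directed therapy text gives continuous 24-hour wear on days 1 and 2 and starts 12-hour wear on day 3. The SAP assessment schedule also gives 24 hours for the increase step. Only the day-2 part of the label is wrong.

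**The case against.** The strongest reply is that the Figure 5a bullets summarise and the renal section governs. Much of this stands. The trigger, the first cut and the hold for stable creatinine all agree. The missing recheck time is an omission, because waiting for a 30% fall presupposes further measurements. Protocol section 7 also allows study medication to be adjusted or suspended for acute kidney injury. That is a general permission, however. It sets no dose, and it does not say which rule applies when creatinine is still rising.

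On diuretics, the reply is that physician discretion is the dominant statement, so the mandatory cut is the outlier. That is a fair reading. Which rule governs is a clinical choice for the sponsor.

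Some stronger readings are tempting, but the documents do not support them.
- **A recheck delayed by up to 24 hours.** The routine schedule reads "Periodical measurements of electrolytes (sodium, potassium) and creatinine at study inclusion, every 24 to 72 hours during the first week and at discharge", and 72 h exceeds the renal section's 48 h by 24 h. This needs a clinician to ignore the renal section and apply the routine schedule to a patient with acute renal injury. Nothing in the protocol says to do that.
- **A competing renal rule in the control arm.** Study Therapy Control Group says "In these cases, the daily dosage of oral therapy may be reduced or stopped temporarily until the patient is stabilized". That wording concerns ACE-inhibitors or ARBs already prescribed on admission. It is not a rule for renal injury arising in hospital.
- **A day-2 patch dosing error.** The text states the wear time clearly, so the label is a slip.
- **Different conduct at sites, or an effect on results.** The documents show neither.

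**Conclusion.** The Figure 5a bullet is wrong as written, and the point is minor. It applies to intervention-arm patients whose creatinine has doubled and still rises after the first 50% cut. For them the two rules leave 50% and 25% of the ACE-inhibitor/ARB dose after one further step. The diuretic conflict is real but secondary, and it is confined to patients with renal injury.

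The conclusion rests on reading a rise of more than 100% and a doubling as the same trigger, and on there being no stated precedence between the sections. The documents give no frequency for either situation, so the number of patients affected cannot be estimated. Nothing follows for the primary endpoint, power or analysis.

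**What to change.** 1. **Main change.** Replace the Figure 5a bullet on a rise above 100% with the renal section's rule: cut the ACE-inhibitor/ARB by 50%; recheck creatinine at 24 to 48 h; if it is still rising, cut a further 50% every 48 h until it begins to decline; hold if it is unchanged or down by less than 30% from peak; resume the schedule after a fall of at least 30% from peak.
2. **Diuretics.** The sponsor chooses one of two routes. Either add a renal-injury exception in the Protocol Summary, the Important Treatment Rules, General Procedure for Both Groups and SAP section 1, or reword the cut in the renal section as a recommendation. Editing the Figure 5a bullet alone would leave three statements in conflict.
3. **Clerical.** In the same edit, point the references to Figure 4 and Figures 4a/4b at the matching Figure 5 schedules, and label the day-2 patch columns in mg per 24 h.

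The cost is a short text amendment and one clarification to sites. Because treatment rules change, the text would go to the ethics committees named in Protocol section 10.2. Design, sample size and analysis are untouched. The value of the site letter depends on how much enrolment remains, which the documents do not state. Recruitment began in November 2007 (Protocol section 9) and the SAP is partly in the past tense, so the letter may come late.
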